2.0 Scientific Endpoints

2.1 Describe the scientific endpoint(s), the main result or occurrence under study.

*NOTE: Scientific endpoints are outcomes defined before the study begins to determine whether the objectives of the study have been met and to draw conclusions from the data. Include primary and secondary endpoints. Some example endpoints are: reduction of symptoms, improvement in quality of life, or survival. Your response should **not** be a date.*

Response: Our primary end-point are predictive. Our first primary end-point will have been met if baseline measures of personality, as measured by the NEO-Five Factor Inventory (NEO-FFI), will predict overall cognitive improvement following rehabilitation. Likewise, our second primary end-point will have been met if baseline measures of brain connectivity predict specific improvements in cognitive sub-domains, following rehabilitation. Cognitive improvement will be measured according to changes from visit 1 to visit 2 for the following neuropsychological tests: Symbol Digit Modalities Test (SDMT), California Verbal Learning Test 2nd Edition (CVLT), Brief Visuospatial Learning Test Revised (BVMT-R), MS Neuropsychological Screening Questionnaire (MSNQ), Delis-Kaplan Executive Function System (DKEFS) Sorting Test, Tower of London (TOL), Elithorn's Perceptual Maze Test (EPMT).

	Day 0 (Visit 1)	Day 90 (Visit 2)
NEO Five Factor Inventory (NEO-FFI)	X	X
Symbol Digit Modalities Test (SDMT)	X	X
California Verbal Learning Test Second Edition (CVLT)	X	X
Brief Visuospatial Memory Test Revised (BVMT)	X	X
MS Neuropsychological Screening Questionnaire (MSNQ)	X	X
Delis Kaplan Executive Function System Tower Test (DKEFS-TT)	X	X
Delis Kaplan Executive Function System Sorting Test (DKEFS-ST)	X	X
Elithorn's Perceptual Maze Test (EPMT)	X	X
Multiple Sclerosis Quality of Life (MSQoL)	X	X
Beck Depression Inventory Fast Screen (BDI-FS)	X	X
Fatigue Severity Scale (FSS)	X	X

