In order to address our second goal, we will use a multi-parametric approach in which we account for cerebral pathology, such as regional gray matter atrophy, microstructural white matter damage, lesion volume and localization, white matter tract integrity and structural connectivity, and resting state functional connectivity. We will apply network-based analysis, where appropriate, in order to account for network-level organization of the brain. These methods of analysis are well-suited for elucidating patterns of insult which lead to changes in complex emergent phenomenon such as higher level cognition.

Our results may provide foundation for better directing rehabilitation and behavioral treatments. For instance, a short questionnaire could be used to identify patients whose personality profile puts them at greater risk for unfavorable disease progression. An understanding of this risk could help direct efforts which mitigate against these unfavorable outcomes. Similarly, baseline patterns of cerebral pathology could also be employed to predict responses to the cognitive and other behavioral interventions. There is a burgeoning interest in personality trait adaptation and personalized health plans among health care agencies²² and we believe our research will contribute meaningfully to this growing field of interest.

3.2 Include complete citations or references.

Response:

2. McCrae RR. Trait psychology and culture: exploring intercultural comparisons. *J Pers*. 2001;69(6):819-846.
doi:10.1037/0022-3514.52.1.81.

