17.0 Data Management and Analysis

17.1 *Describe the data analysis plan, including any statistical procedures. This section applies to both quantitative and qualitative analysis.*

Response:

Statistical analyses will be performed using SPSS 22.0 (IBM Inc., Armonk, NY, USA) and R 3.4.1 (The R Foundation).

[1a] Determine whether low Conscientiousness predicts lesser overall cognitive improvement following cognitive rehabilitation in people with MS. The question of whether Conscientiousness predicts successful intervention will be addressed using baseline measures of trait Conscientiousness and cognitive performance before and after rehabilitation. We will assess linear relationships between baseline trait Conscientiousness and overall magnitude of cognitive improvement using linear regression models. Cognitive improvement will be measured according to differences in cognitive scores between baseline assessment during visit 1 and post-rehabilitation assessment at visit 2. In order to summarize results across all cognitive measures, test scores will be converted to normalized z-scores and averaged together.

1b] Determine whether the impact of Conscientiousness on cognitive rehabilitation is moderated by executive function and treatment adherence. In order to address the question of whether or not adherence and executive function moderate the impact of Conscientiousness on intervention success, we intend to add interaction parameters to the linear regression analysis described for aim 1a.

For instance, we will calculate the interaction variable between Conscientiousness and DKEFS-ST (executive function) and include it in our regression models.

[2] Identify structural and functional brain connectome characteristics which predict successful improvement in sub-domains of cognition following rehabilitation. In order to identify brain connectome characteristics which, predict specific responses to sub-domains of cognition following rehabilitation, we intend to employ linear machine/statistical learning techniques, such as partial least squares regression. The correct statistical learning models will be identified at the time of analysis in order to produce the most appropriate predictions. Models will be selected according to the distribution and dimensionality of our connectome variables. Following training of the predictive models, fit of the models will be assessed using k-fold cross validation.

17.2 If applicable, provide a power analysis.

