[2] Identify structural and functional brain connectome characteristics which predict successful improvement in sub-domains of cognition following rehabilitation. In order to identify brain connectome characteristics which predict specific responses to sub-domains of cognition following rehabilitation, we intend to employ linear machine/statistical learning techniques, such as partial least squares regression. The correct statistical learning models will be identified at the time of analysis in order to produce the most appropriate predictions. Models will be selected according to the distribution and dimensionality of our connectome variables. Following training of the predictive models, fit of the models will be assessed using k-fold cross validation.

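### Aim 2 does not say that tuning, choice of imaging blocks and feature reduction stay inside the cross-validation folds, so accuracy for the second primary end-point may be inflated

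*SAP*

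**What the plan says.** Protocol section 2.1 gives aim 2 primary status: "our second primary end-point will have been met if baseline measures of brain connectivity predict specific improvements in cognitive sub-domains, following rehabilitation".

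The analysis is in the aim 2 paragraph of the SAP, with essentially the same text in Protocol section 17.1. It has four parts.

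- Method: "we intend to employ linear machine/statistical learning techniques, such as partial least squares regression". PLS is only an example.
- Timing and purpose of model choice: "The correct statistical learning models will be identified at the time of analysis in order to produce the most appropriate predictions".
- Criterion for that choice: "Models will be selected according to the distribution and dimensionality of our connectome variables".
- Validation: "Following training of the predictive models, fit of the models will be assessed using k-fold cross validation".

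The candidate predictors are described in Protocol section 3.1 and cover several imaging blocks: "regional gray matter atrophy, microstructural white matter damage, lesion volume and localization, white matter tract integrity and structural connectivity, and resting state functional connectivity". Protocol section 5.1 sets enrolment at 50.

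Neither document gives the number of features, a candidate list, a rule for the number of components or a penalty, the number of folds, nesting, repeats, a hold-out sample, an accuracy metric, a permutation test or a numerical criterion for success.

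**The concern.** Cross-validated accuracy is an honest out-of-sample figure only if every step that used the outcome is repeated without the held-out participants. PLS needs a number of components, a penalised model needs a penalty, and several imaging blocks raise the question of which ones enter. These choices are commonly made by looking at how well the outcome is predicted. If they are made once on all participants and the chosen model is then cross-validated, the held-out participants have already influenced it.

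The k-fold result is the only evidence the plan offers for its second primary end-point. The sample is small and the predictors are many, which is where this kind of optimism is largest. The end-point could then be declared met on noise.

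**Working it through.** **The plan's own figure.** There is none for aim 2. The sample size of 41 in Protocol section 17.2 concerns Conscientiousness, not the connectome. It is used below only as a second, smaller sample size.

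**What the text settles.** The predictor-based criterion governs which model is selected. The validation sentence governs how fit is assessed. No sentence says how the number of components, a penalty, the imaging blocks or a reduced feature set is chosen, or whether that happens inside or outside the folds.

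**How much it could matter.** Two null simulations were coded separately, with the outcome generated independently of the connectome. From the documents: n = 50 and n = 41, linear learners including PLS, and several imaging blocks. Everything else is assumed.

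- Simulation A: 4,005 connections per modality; two modalities and their union, each with PLS (1–6 components) and 4 ridge penalties, so 3 × (6 + 4) = 30 candidates; 10 folds.
- Simulation B: 300 correlated features per block; 1 or 4 blocks, each with PLS (1–5 components) and 4 ridge penalties, so 9 or 36 candidates; 5 folds; 171 to 621 replicates per setting.

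The accuracy measure is the correlation r between observed and held-out predicted outcome. The reference is the usual two-sided 5% critical value, r = t/√(t² + n − 2):

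- n = 50: t = 2.011, r = 2.011/√(4.043 + 48) = 0.279
- n = 41: t = 2.023, r = 2.023/√(4.091 + 39) = 0.308

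The plan sets no such cut-off; it serves here only as a yardstick. Exceeding it on the positive side has a nominal rate of 2.5%.

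Simulation B, mean r and share of noise data sets above the critical value:

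| n, candidates | One model fixed without the outcome | Best candidate, reported from one loop | Nested | Top 20 features screened on the full sample |
|---|---|---|---|---|
| 41, 9 | −0.033, 6.1% | 0.040, 8.7% | −0.045, 5.5% | 0.335, 61.5% |
| 50, 9 | −0.030, 5.2% | 0.045, 10.1% | −0.045, 3.9% | 0.306, 59.5% |
| 41, 36 | −0.027, 4.4% | 0.230, 28.0% | −0.022, 6.7% | 0.338, 57.8% |
| 50, 36 | −0.051, 1.8% | 0.222, 31.0% | −0.039, 8.2% | 0.284, 54.4% |

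Inflation of mean r against nested validation:

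- Best of 9: 0.040 + 0.045 = 0.085 (n = 41) and 0.045 + 0.045 = 0.090 (n = 50).
- Best of 36: 0.230 + 0.022 = 0.252 (n = 41) and 0.222 + 0.039 = 0.261 (n = 50).

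The Monte Carlo standard error for the 31.0% is √(0.31 × 0.69/171) = 3.5 points.

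Simulation A at n = 50 gave 12% and 19% (two runs) for the best of 30 with correlated connections, against 2–7% for one fixed model and about 6% for nested validation. With fully independent connections the best of 30 gave 3%, so choice of model alone added little. Screening the top 1% of connections on the full sample gave mean null r of 0.75 (correlated) to 0.92 (independent), against 0.00 when screening was redone inside each fold.

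**A check without the 0.279 cut-off.** Take Q² = 1 − Σ(y − ŷ)²/Σ(y − ȳ)², where a value above 0 means better than predicting the mean. In simulation B the best candidate by Q² was above 0 in 17–19% of noise data sets with 9 candidates and 42–47% with 36. The nested procedure, which tuned on r, was above 0 in 2.5–5.8%. The direction is the same.

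**The case against.** The strongest reply is that the plan states a harmless criterion. The distribution and dimensionality of the connectome variables are properties of the predictors, and the plan nowhere names the outcome or cross-validated accuracy as the basis for selection. The simulation supports this: a model fixed without the outcome gave mean r between −0.03 and −0.05, with no inflation. That stands for the choice of model family. It does not settle the component count, penalty, imaging blocks or feature reduction, which the criterion does not mention.

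A reader might infer that the plan commits to a single, un-nested loop with tuning done outside it, so that the reported accuracy is inflated. The documents do not support that. They say only that k-fold cross-validation will be used and are silent on nesting. Placing it after training suggests an order of steps but does not fix where tuning occurs, and k-fold cross-validation itself refits the model in each fold. Producing appropriate predictions is also not the same as choosing whatever predicts best.

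The magnitudes are open to challenge as well. The documents give no feature count. Screening against the outcome is never mentioned, and PLS can handle many predictors without it, so the largest figures describe an error the plan does not announce. For the same error the two simulations differ widely (mean null r 0.28–0.34 against 0.75–0.92). The effect of model choice ranges from none to large, depending on the correlation structure and the number of candidates. These objections limit what can be said about size. They do not supply the missing rule.

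**Conclusion.** The concern holds as a gap in specification. For a primary end-point with at most 50 participants, the plan leaves the model open and does not require outcome-dependent choices to be made inside the folds. Accuracy may therefore be materially inflated; it cannot be said that it will be.

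As an illustration, reporting the best of 9–36 candidates from one loop put about 3–31% of noise data sets above the critical r, against about 4–8% with nested validation. The lower end is no excess at all. Full-sample screening on the outcome would give a mean null r of about 0.3–0.9, but the plan does not mention such screening. All these figures rest on assumed feature counts, correlation, candidate lists and fold numbers, on a single outcome, and on a cut-off the plan does not set. If every choice were made on the predictors alone, plain k-fold would be adequate. The change below is a cheap improvement that removes the doubt.

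**What to change.** In the aim 2 paragraph of the SAP and in Protocol section 17.1, before analysis:

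- Fix a short list of candidate models, with the range of components or penalties and the imaging blocks to be considered.
- Replace plain k-fold with nested, preferably repeated, k-fold cross-validation (for example 10 outer and 5 inner folds). State the number of folds and the accuracy metric.
- State that every outcome-dependent step (choice among candidates, components or penalty, imaging blocks, any feature reduction) is redone within each outer training fold.
- Judge the second primary end-point only on outer-fold held-out predictions.
- If a permutation test is used, rerun the whole nested procedure for each permutation. This matters because even nested validation exceeded the ordinary critical value in 4–8% of noise data sets, against a nominal 2.5%.

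The cost is SAP wording and computing time, with no new data. The reported accuracy will probably be less favourable. Made after the results are seen, the change could no longer be shown to be independent of them.

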5.0 Local Number of Subjects

5.1 *Indicate the total number of subjects that will be enrolled or records that will be reviewed locally.*

Response: We will recruit 50 subjects with multiple sclerosis who are already enrolled in CEG-MS study.

5.2 *If applicable, indicate how many subjects you expect to screen to reach your target sample (i.e. your screen failure rate).*

Response:

We expect that potential participants to be enrolled through the CEG-MS study for suitability for the study. Subjects who agree to participate and pass screening requirements will be enrolled in the study.

5.3 Justify the feasibility of recruiting the proposed number of eligible subjects within the anticipated recruitment period. For example, how many potential subjects do you have access to? What percentage of those potential subjects do you need to recruit?

Response: This research will be conducted through the Buffalo Neuroimaging Analysis Center (BNAC) group. We expect to recruit subjects from the CEG-MS study database. Based on our targeted population, we believe there is a sufficient number of potential participants to meet participant target of 50 in adherence to the protocol.

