20.2 *Describe any procedures for orderly termination.*

NOTE: Examples may include return of study drug, exit interview with clinician. Include whether additional follow up is recommended for safety reasons for physical or emotional health.

Response: In the event of early termination/withdrawal from the study, an exit interview will be conducted by the PI, treating clinician or trained members of the research team.

20.3 Describe procedures that will be followed when subjects withdraw from the research, including retention of already collected data, and partial withdrawal from procedures with continued data collection, as applicable.

Response: Participation in this study is voluntary. Referred patients may refuse to participate without penalty and such refusal will not prejudice future treatment or benefits at the Jacobs Neurological Institute (JNI) or Buffalo Neuroimaging Analysis Center (BNAC). Patients will be free to discontinue participation in the study at any time without fear of penalty or loss of medical care or loss of any benefits to which you may otherwise be entitled. If a subject chooses to withdraw from the study, the data collected up to the time of withdrawal will continue to be used, but the subject will no longer be contacted and no further data will be collected.

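### Aim 2 permits one random k-fold partition of at most 50 people to decide the second primary end-point; the partition should be repeated and averaged, with a recorded seed

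*SAP*

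**What the plan says.** Protocol 2.1 makes aim 2 a primary end-point: "our second primary end-point will have been met if baseline measures of brain connectivity predict specific improvements in cognitive sub-domains, following rehabilitation". It gives no metric, threshold, test or interval by which prediction would be judged.

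The SAP (aim 2) names the model class only by example: "we intend to employ linear machine/statistical learning techniques, such as partial least squares regression". The final choice is deferred: "The correct statistical learning models will be identified at the time of analysis in order to produce the most appropriate predictions". The assessment is then one sentence: "Following training of the predictive models, fit of the models will be assessed using k-fold cross validation". Protocol 17.1 carries the same text.

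On numbers, Protocol 5.1 says: "We will recruit 50 subjects with multiple sclerosis who are already enrolled in CEG-MS study". After a withdrawal, Protocol 20.3 says that "the subject will no longer be contacted and no further data will be collected", so anyone who leaves before visit 2 has no change score. Fifty is therefore an upper limit for this analysis.

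Neither document states k, the number of repeats, a seed, a fit metric, a success threshold, a permutation test or a separate test sample.

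**The concern.** K-fold cross-validation deals participants to folds at random. In a small sample the resulting fit depends on the deal as well as on the data and the model. If one deal is used, and the fit it produces is the only evidence for a primary end-point, two analysts with the same data, model and metric can report different answers. With no seed recorded in advance, nobody can later show that the reported partition was the first one drawn.

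This noise is distinct from the optimism that comes from choosing a model on the data being predicted. Moving all selection inside the folds removes that optimism but leaves the dependence on the deal.

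**Working it through.** **1. The plan's own figure.** There is none for aim 2. The only sample-size figure is 41, in Protocol 17.2, for the Conscientiousness question. Reading the 0.38 effect size as a correlation, with an assumed one-sided 5% level and 80% power, Fisher's z gives n = (2.486 / atanh 0.38)² + 3 = (2.486 / 0.4001)² + 3 = 41.6, close to the stated 41. It does not bear on aim 2. I use 41 only as a lower completion number: (50 − 41)/50 = 18% loss.

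**2. Fold sizes.** With k = 5, a held-out fold has 50/5 = 10 people, or about 8 of 41. With k = 10 it has 5, or about 4 of 41. Both values of k are assumptions.

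**3. Simulation set-up (assumed, since the documents give none of it).** There are 100 connectome features generated from 5 latent factors, and the outcome depends on one factor with true R² of 0, 0.15, 0.30 or 0.50. The model is partial least squares with 2 components. Each setting has 60 data sets, each re-partitioned 60 times with data and model fixed. Two illustrative success rules were used:
- Rule A: cross-validated R² above 0.
- Rule B: correlation of predicted with observed values above the two-sided 5% critical value (0.279 at n = 50, 0.308 at n = 41). With no signal, this rule was met in 3–6% of partitions.

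If a share q of partitions meets the rule in a given data set, two random partitions disagree with probability 2q(1 − q). This is averaged over data sets.

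**4. Results at weak to moderate signal.**

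| n | True R² | k | SD of cross-validated R² over partitions | Disagreement, rule A | Disagreement, rule B |
|---|---|---|---|---|---|
| 50 | 0.15 | 5 | 0.115 | 13.0% | 19.7% |
| 50 | 0.15 | 10 | 0.076 | 8.2% | 9.8% |
| 50 | 0.30 | 5 | 0.086 | 13.7% | 7.2% |
| 50 | 0.30 | 10 | 0.056 | 14.4% | 4.5% |
| 41 | 0.15 | 5 | 0.135 | 12.4% | 12.5% |
| 41 | 0.15 | 10 | 0.096 | 7.4% | 10.7% |
| 41 | 0.30 | 5 | 0.100 | 19.6% | 15.5% |
| 41 | 0.30 | 10 | 0.074 | 8.6% | 9.8% |

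The range is 4.5–19.7%, or about 5–20%. Over the same n and k, disagreement is 1.5–6.0% with no signal and 0.3–5.3% at true R² of 0.50. The quantity 2q(1 − q) lies between 0 and 0.5, so its SD is at most 0.25 and each cell has a Monte Carlo standard error of at most 0.25/√60 = 0.03. The range should be read, not single cells. A separate simulation with 200 features at n = 50 and true R² of 0.15–0.30 gave about 10–14% at k = 5 and 6–10% at k = 10.

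**5. Effect of averaging.** Partitions are drawn independently given the data, so averaging 100 divides the partition SD by √100 = 10. In a second run (k = 5, true R² 0.15 and 0.30, n = 50 and 41, 40 data sets each) the single-partition SD of 0.086–0.148 becomes 0.009–0.015. Disagreement between two single partitions was 13–20% (rule A) and 8–18% (rule B). Between two independent 100-repeat runs it was 0 or 1 data set in 40 per setting. Pooled, that is 2/160 = 1.3% for rule A and 1/160 = 0.6% for rule B.

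**6. Power.** In a simulation with n = 50, 300 features and 300 data sets, success meant a cross-validated correlation above the 95th percentile under no signal. Averaging 20 repeats raised power from 32% to 44% and from 74% to 84% at k = 5, but by only 1–2 points at k = 10. Each estimate has a standard error of about 2–3 points (for example √(0.44 × 0.56/300) = 0.029).

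**The case against.** The strongest reply is that the documents never say one split. A reader might infer that the plan commits to a single partition, but the text is silent. Repeated k-fold would comply with it, and so would leave-one-out, which has no random assignment at all. This stands. The defensible statement is that the plan permits a single partition and that unqualified k-fold is ordinarily read that way.

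The second reply is that no rule for meeting the end-point exists, so any changed verdict is a change under an assumed rule. The late choice of model and the missing metric and threshold give two analysts earlier and larger reasons to differ. This also stands: those gaps are at least as serious. It does not dispose of the point, because the simulations fixed model, metric and threshold in advance and the verdict still moved with the deal.

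Two further inferences should be resisted:
- With 1,000 features, 14–42% of data sets had a success share between 10% and 90% over partitions. A reader might take that for the chance that two analysts disagree. It is not: at the edge of that window, two partitions disagree with probability 2 × 0.1 × 0.9 = 18%, and the other data sets contribute less.
- A reader might conclude that a single partition costs this trial material power. That was seen only at k = 5. At k = 10 the gain is within simulation error, and the documents do not state k.

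**Conclusion.** The point holds as a weakness of specification with a measurable consequence. The only assessment named for the second primary end-point is k-fold cross-validation in at most 50 people, without repeats or a seed, and a single random partition would satisfy it. Under the assumptions set out above, two such partitions of the same data disagree in about 5–20% of cases at a true R² of 15–30%, about 2–6% with no signal, and 0–5% at a true R² of 50%. These figures show a range, not a forecast for this trial: feature count, signal structure, number of components, k and success rule are all assumed.

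The main benefit of averaging is a verdict that another analyst can reproduce. The power benefit runs from a few points to about 12 at k = 5 and is about 0–2 points at k = 10. The issue does not invalidate the trial; it is an improvement that costs nothing in participants or data.

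**What to change.** In SAP aim 2 and in Protocol 17.1, replace the reference to k-fold cross validation with: *k-fold cross validation repeated over at least 100 random partitions with a recorded seed, with all model selection and tuning carried out inside the folds*. State k and the fit metric in the same place; without them the repeated statistic is still not fixed.

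Then add three short statements:
- The end-point statistic is the mean fit over repeats.
- It is compared with a permutation reference distribution of the same repeated statistic, so that statistic and reference carry the same averaging.
- The spread over partitions is reported as split noise only, not as a confidence interval. It does not reflect the sampling error from 50 or fewer people, and a narrow spread must not be read as precision.

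The cost is a few lines of text and computing time, chiefly for rerunning the whole repeated procedure in each permutation. No participants, visits or additional data are needed.
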